Resolution of Depression for Some with ART: Our previous work in Uganda has shown that while a portion of HIV-infected people remain depressed even after starting ART, a large percentage resolve with ART alone. In our previous studies in cryptococcal disease, 65% (N=217) of 325 cryptococcal survivors were depressed via the CES-D scale at time of ART initiation and of those depressed, at 8 weeks 47.5% (N= 103) were no longer depressed, 31% (N=67) remained depressed, and 21.7% (N=47) had died or were lost to follow up (unpublished data). Similarly, 59% in those with cryptococcal antigenemia (N=207) were depressed pre-ART compared to 30% in 125 HIV-infected controls pre-ART with a mean CD4 count of 242 ± 119 cells/ μ L.³⁸ In those with meningitis, we followed depression via CESD and found a significant portion of the depression resolved with HIV therapy but no depression specific therapy. Similarly our co-mentor [name] recently presented a poster at CROI from a subset of participants in the Rakai cohort with available follow up data.³⁹ The researchers found among 333 people with HIV and ART naïve, 22% (N=73) were depressed via CESD score at baseline and 8.4% (N=28) 2 years later. Thus, in this cohort 38% (28/73) had persistent depression at 2 years with HIV therapy alone. [name] co-authored another study looking at ART naïve, HIV-infected Ugandans and found that the rate of persistent depression was 25% over 1 year.⁴⁰

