4. TREATMENTS OF SUBJECTS

4.1. Allocation to Treatment/Group

The first half of the depressed participants (100 subjects) will be in the observational cohort.

The second half of the depressed participants (100 subjects) will be in the intervention cohort and receive group psychotherapy.

A second non-depressed control group (100 subjects) will be added for another observational cohort.

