8. DATA ANALYSIS/STATISTICAL METHODS

8.1. Sample Size Determination

Depression Intervention:

We will power for a reduction in IL-6 between those with persistent and resolved depression at 26 weeks. Based on our systematic review, the reduction in depression score for psychotherapy is 73% from baseline.³² However response rates vary. Another review found the score reduction was 20% when compared to controls.⁴² We then calculated a range of possible sample sizes seen in **Statistics Plan**.

Assuming that 25% of the psychotherapy group will have persistent depression at week 26 (with equal sample sizes, 80% power, and two-sided alpha = 0.05) and I want a delta of .5, we need a total sample size of 168

participants. The prior study had a 22% non-completion rate for group therapy.³⁴ To account for non-completion and up to a 5% loss to follow-up, I estimate a sample size of 200 participants.

Subject Recruitment/Number needed to screen

[figure not shown]
I postulate that the baseline depression rate in these ART naïve subjects would be about 25%.⁴³ Thus we would need to screen 800-1000 HIV+ people.

The non-depressed control group will come out of those screened and not add to the total number screened.

These will be enrolled from the Infectious Disease Institute or three clinics that refer to it. As noted in the preliminary data section, we are currently working on a study in those found clinics and have found we can get about 15 new patients with CD4 <100 cells/uL a month (unpublished data). Our experience is that there are many more presenting with higher CD4 cells/uL counts, or about 150 new individuals a month. Taken these patient sources we estimate we could screen 800-1000 participants over 2.2 years from our 4 clinics and given not all participants will agree to participate we estimate that we can enroll the group over 2.5 years.

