8.2. Analysis of Endpoints

- 1) *Effect of Group Support Psychotherapy:* We will compare the proportion of baseline depression with the proportion of persistent depression at week 26. We will use the PHQ-9 as a continuous variable, with changes from baseline to week 26.
- 2) *Effect of biomarkers on persistent vs. resolved depression:* We will compare those with persistent depression (PHQ-9 ≥ 5 at week 26) versus resolved depression (PHQ-9 < 4 at week 26). We will assess baseline demographic and HIV parameters as well as log₂-transformed plasma cytokines from week 0, week 26, and the change in biomarker values from week 0 to week 26. We will use Benjamini-Hochberg adjustment for multiple comparisons for the biomarkers unrelated to our *a priori* hypothesis (i.e. IL-6 association with persisting depression). If the distribution between groups is unbalanced for an important factor (e.g. age, sex as biological variable, anti-depressant use, HIV viral load), we will adjust as needed for differentially distributed variables between the cohorts. We will consider sex as a biological variable in our analyses, considering differential effects in women vs. men.
- 3) *Effect of biomarkers on depressed vs non-depressed control group:* We will compare those never depressed (PHQ-9 < 5) and those depressed at baseline and at 26 weeks. We will also group those never depressed with those with resolved depression (PHQ-9 < 5 at week 26) and compare with those with persistent depression (PHQ-9 > 4 at week 26). We will assess baseline demographic and HIV parameters as well as log₂-transformed plasma cytokines from week 0, week 26, and the change in biomarker values from week 0 to week 26. We will use Benjamini-Hochberg adjustment for multiple comparisons for the biomarkers unrelated to our *a priori* hypothesis (i.e. IL-6 association with persisting depression). If the distribution between groups is unbalanced for an important factor (e.g. age, sex as biological variable, anti-depressant use, HIV viral load), we will adjust as needed for differentially distributed variables between the cohorts. We will consider sex as a biological variable in our analyses, considering differential effects in women vs. men.

*Depression Defined as PHQ-9 score 5-19 (severely depressed excluded)

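### Section 8.2 item 2 leaves a week-26 PHQ-9 score of 4 in neither group of the powered IL-6 comparison; treatment cohort should also be a fixed covariate

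*Combined protocol and SAP*

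**What the plan says.** Section 8.1 fixes the powered comparison: "We will power for a reduction in IL-6 between those with persistent and resolved depression at 26 weeks". It sizes the study from one persistence figure: "Assuming that 25% of the psychotherapy group will have persistent depression at week 26".

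Section 8.2 item 2 defines the two groups. Persistent is a week-26 PHQ-9 of at least 5, and resolved is a week-26 PHQ-9 below 4. The same analysis in the protocol summary (Statistical Analysis, item 2) uses above 4 and below 5. Section 8.2 item 3, which reuses the resolved group, also has below 5. The summary and the Study Design text place scores up to 4 in the not-depressed category.

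On allocation, section 4.1 puts the first 100 depressed participants in the observational cohort, and then: "The second half of the depressed participants (100 subjects) will be in the intervention cohort and receive group psychotherapy". Section 8.1 expects recruitment to be long: "we estimate that we can enroll the group over 2.5 years". On covariates, section 8.2 item 2 says "If the distribution between groups is unbalanced for an important factor (e.g. age, sex as biological variable, anti-depressant use, HIV viral load"), and then "we will adjust as needed for differentially distributed variables between the cohorts". Treatment cohort is not among the examples.

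**The concern.** The two group definitions in item 2 do not meet. A participant who goes from depressed to a score of 4 has recovered by every other definition in the protocol, yet is left out of the comparison on which the sample size rests. The same person counts as resolved in item 3. An analyst following section 8.2 literally would report two different resolved groups under one name. The people removed are also those nearest the threshold, so the omission is not random with respect to severity.

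The second matter is smaller. Cohort is set by order of enrolment, so it carries both psychotherapy and calendar time. Hypothesis A expects psychotherapy to reduce depressive symptoms, so cohort may be related to who is persistent. If cohort were also related to IL-6 by a route other than depression status, part of the pooled difference would reflect cohort. The plan leaves the choice to adjust for it open, with no threshold.

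**Working it through.** **Cut-offs side by side.** PHQ-9 items are scored 0 to 3 and summed (Appendix 17.1), so totals are whole numbers. Above 4 and at least 5 are therefore the same, as are below 5 and at most 4.

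| Place | Persistent | Resolved or not depressed | Score of 4 |
|---|---|---|---|
| Summary, analysis item 2 | > 4 | < 5 | resolved |
| Summary and Study Design cut-offs | – | ≤ 4 | not depressed |
| Section 8.2 item 3 | > 4 | < 5 | resolved |
| Section 8.2 item 2 | ≥ 5 | < 4 | neither |

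Only section 8.2 item 2 leaves a gap.

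**The plan's own figure.** Inputs from section 8.1: two-sided alpha 0.05, power 80%, delta 0.5 (no SD is given; read as 0.5 SD), 25% persistent, hence a 1:3 ratio.

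- Persistent n = (1 + 1/3) × (1.96 + 0.8416)² / 0.5² = 41.86, rounded up to 42.
- Resolved n = 3 × 42 = 126. Total = 168, as stated.
- Power at 42 vs 126 is 80.1% by the normal approximation and 79.7% by the noncentral t.

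**Effect of losing score 4.** The share of resolved participants scoring exactly 4 is not in the documents; 10–30% is assumed. The noncentrality is 0.5 × √(n₁n₂/(n₁+n₂)), with the difference held at 0.5 SD.

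| Share scoring 4 | Dropped | Groups | Power |
|---|---|---|---|
| 0% | 0 | 42 vs 126 | 79.7% |
| 10% | 13 | 42 vs 113 | 78.5% |
| 20% | 25 | 42 vs 101 | 77.2% |
| 30% | 38 | 42 vs 88 | 75.4% |

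Removing near-threshold participants could also widen the contrast. At 42 vs 88, a difference of 0.53 SD gives 80.1%, so the net effect on power could go either way.

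**Is item 2 pooled over cohorts?** The plan does not say so outright. Objective 2 refers to the same population as objective 1, item 2 is not split by cohort, and 168 is reached only as 42 + 126 overall. The psychotherapy cohort alone, at 25 vs 75, would have 58% power. Pooling is a strong inference.

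**Possible bias from cohort.** Bias = (observational share of the persistent group − observational share of the resolved group) × separate cohort effect on IL-6. Assume 84 per cohort and 25% persistence with psychotherapy. For the observational cohort, section 1.2 offers two outside figures: "the rate of persistent depression was 25% over 1 year" and "in this cohort 38% (28/73) had persistent depression at 2 years with HIV therapy alone".

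- 25% vs 25%: 0.500 − 0.500 = 0, so no bias whatever the cohort effect.
- 38% vs 25%: persistent 31.92/52.92 = 0.603; resolved 52.08/115.08 = 0.453; gap 0.151 after rounding. With an assumed separate effect of 0.2–0.5 SD, bias is 0.030–0.075 SD.

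**Cost of always including cohort.** Variance factor = 1/(1 − φ²).

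- 25% vs 25%: φ² = 0, factor 1.00; power 80.1% either way.
- 38% vs 25%: φ² = 0.13² × 0.25 / (0.315 × 0.685) = 0.0196, factor 1.02; power 85.3% to 84.6% (normal approximation), or 84.6% to 83.7% by simulation.

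**The case against.** The strongest reply on the cut-off is that below 4 is a slip, since every other passage agrees on below 5. That is very probably so, and it also means the power figures above describe a literal reading that the team may never apply. What stands is that section 8.2 is the full analysis section, and its definition of the powered comparison disagrees with the summary and with the next item.

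On cohort, the reply is that the adjustment rule already covers it. The list of factors is only illustrative and includes a treatment variable (antidepressant use), and the rule speaks of imbalance between groups. Most of this stands. A reader might infer that type I error rises to 5.4–7.2% under this plan. The documents do not support that. Those rates belong to an analysis with no adjustment at all. They also need a separate cohort effect of 0.2–0.5 SD that appears nowhere in the protocol, and a 38% persistence taken from a two-year CES-D cohort on HIV therapy alone. Here the observational cohort is referred for SSRIs and assessed by PHQ-9 at 26 weeks. In simulation of the worst of these cases (0.5 SD, 10,000 runs), error was 7.2% unadjusted. It was 5.4% if cohort was added when its imbalance had p < 0.05, 5.1% at p < 0.10 or at a standardised difference above 0.1, and 5.2% if cohort was always included. So the existing rule does nearly all the work, provided cohort is regarded as an important factor. The plan does not commit to that.

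A reader might also infer a multiplicity problem, because the exemption of IL-6 from Benjamini-Hochberg adjustment gives no time point while item 2 lists week 0, week 26 and change. That does not hold. The exemption is tied to the a priori hypothesis, and sections 2.2 and 8.1 place that hypothesis at week 26.

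**Conclusion.** The cut-off in section 8.2 item 2 is an error as written, and it sits in the definition of the powered comparison. Finding it needs no assumption. Its effect on power is modest and uncertain: a loss of about 1 to 4 points if 10–30% of resolved participants score 4 and the difference stays at 0.5 SD, possibly offset by a wider contrast. The main harm is that one section defines two different resolved groups.

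Naming cohort as a covariate is a worthwhile secondary improvement, and the plan is not defective without it. It rests on the inference that item 2 pools both cohorts. Bias arises only if persistence differs between cohorts, cohort affects IL-6 separately from depression status, and the analyst does not treat cohort as important.

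**What to change.** 1. Reconcile section 8.2 item 2 with the protocol summary, section 8.2 item 3 and the stated PHQ-9 categories, so that persistent and resolved are complementary and a score of 4 falls in exactly one group. Use the same definition wherever the two groups recur, including the virologic outcome. This is a wording change. If the boundary used everywhere else is adopted, it returns the omitted participants and restores the 42 vs 126 split behind the stated 168.

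2. State that week-26 log2 IL-6, persistent versus resolved, will be analysed by linear regression with treatment cohort always included, and keep the existing rule for the other covariates. The sample size stays at 168 (200 with losses). The cost is under 1 point of power at 25–38% observational persistence, and 2.3 points if that persistence were 50% (an assumption). If psychotherapy acted on depression only through IL-6, simulation at a within-cohort difference of 0.5 SD gives a loss of 0.6–2.2 points, and the adjusted model still recovers 0.50 SD.

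Both changes should be made before outcome data are examined, because the study is open-label.

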4) Baseline Cytokine Analysis: As a secondary outcome, subjects will be categorized into baseline groups of mild depression versus moderate or above depression. We will compare baseline plasma biomarker levels by group via linear regression of log2 transformed data. Any demographic covariates associated with depression will be included in the regression model. We will also compare by 9 am cortisol levels. We will assess whether age or sex are associated with biomarker responses.

5) Virologic Outcomes: As a secondary outcome, proportions of those with 26-week virologic suppression will be compared by those with persisting depression vs. resolved using Fisher's Exact test.

6) Depression Scale Comparison: We will compare prevalence of depression using the PHQ-9 and the HDRS. We will compare the proportions of those depressed at baseline and 26 weeks using McNemar's test.

7) Social Factors and Stress Assessment: We will analyze social factors and the STRAIN stress and adversity tool scores by baseline depression and control groups as well as those with persistent depression at 26 weeks using linear regression.

LIST OF ABBREVIATIONS AND DEFINITIONS OF TERMS

AE	Adverse events
ART	Antiretroviral Therapy
CD4	CD4+ T helper Cells
CRF	Case report form
HRDS	Hamilton Rating Depression Scale
HIV	Human Immunodeficiency Virus
IDI	Infectious Diseases Institute
IL-6	Interleukin-6
IRB	Institutional Review Board
KCCA	Kampala Capital City Authority

MU-JHU	Makerere University – John's Hopkins University Core Laboratory
PHQ-9	Patient Health Questionnaire 9 Item Depression Screening Tool
PI	Primary Investigator
SAE	Serious Adverse Event
SSRI	Selective Serotonin Reuptake Inhibitor
STRAIN	Stress and Adversity Inventory

TABLE OF CONTENTS

LIST OF ABBREVIATIONS AND DEFINITIONS OF TERMS	6
1. INTRODUCTION	10
1.1. Disease Setting/Patient Population	10
1.2. Background and Rationale.....	10
2. STUDY OBJECTIVES AND ENDPOINTS.....	12
2.1. Objectives	12
2.2. Study Hypothesis	12
3. SUBJECT SELECTION	13
3.1. Inclusion Criteria	13
3.2. Exclusion Criteria.....	14
4. TREATMENTS OF SUBJECTS.....	14
4.1. Allocation to Treatment/Group	14
4.2. Drug Supplies.....	14
5. STUDY PROCEDURES	14
5.1. Screening.....	14
5.2. Study Period.....	15
5.3. Subject Withdrawal.....	15
6. ASSESSMENTS	15
6.1. Safety	15
6.2. Pregnancy Testing	16
6.2.1. Sample Handling.....	16
7. ADVERSE EVENT REPORTING	16
7.1. Adverse Events.....	16
7.2. Serious Adverse Events	16
7.3. Severity Assessment	17

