1.2. Background and Rationale

Depression in HIV is common and causes poor HIV outcomes. Depression prevalence in HIV-infected persons ranges from 13 to 78% as compared to 5% in the general population.^{16, 17} Adherence to antiretroviral medication and subsequently viral suppression is a life-saving treatment in HIV.¹⁸ However, depression has been shown to reduce engagement in care as well as adherence to medication.¹⁹ There is also evidence that depression is associated with poorer levels of viral suppression and even mortality.^{20, 21}

Depression in HIV has negative public health implications. Depression decreases the likelihood that people will engage in HIV care, adhere to treatment, and respond to HIV therapy. Those with depression and HIV are less likely to return to health and remain more likely to transmit the virus.^{22, 23} Because of this, treatment of HIV is an important key to prevention; lower rates of engagement in and adherence to HIV treatment due to depression means others remain at risk.^{24, 25}

Growing evidence shows depression has an inflammatory component. Depression has higher prevalence in neuroinflammatory disorders including stroke, diabetes, and HIV.¹⁴ These conditions alter the blood brain barrier allowing for infiltration of immune cells and increased cytokine signaling. While many diseases make people chronically ill such as hepatitis B, only some have increased prevalence of depression such as HIV. This observation does not suggest that the psychosocial impacts of chronic life-threatening illness do not contribute to depression but does imply that neuroinflammatory effects in diseases such as HIV can be additive or synergistic in the pathogenesis of depression.

Depression in HIV, even when participants have virologic suppression, is often resistant to standard psychiatric treatment, and treatment for depression among people living with HIV is understudied. While there are many treatment modalities for depression, a significant proportion of patients do not respond to treatment.²⁶ Also, while there are a few studies looking at treatment of depression specific in HIV, the data are scant.^{27, 28} More work on depression treatment in those with HIV is needed, particularly in low-income countries in sub-Saharan Africa given the high prevalence of HIV.

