2. STUDY OBJECTIVES AND ENDPOINTS

2.1. Objectives

- 1) Among depressed HIV-infected Ugandans, determine if the resolution of depression at 26 weeks of HIV therapy is improved with group psychotherapy.
- 2) In the same population determine if persistent depression is associated with higher levels of innate inflammation. Also, compare baseline and follow up inflammation among depressed compared to non-depressed control group.
- 3) Evaluate if viral suppression levels at 26 weeks are improved by group psychotherapy.

Endpoints

- 1) Depression score via patient health questionnaire (PHQ-9) at screening (total screened and total enrolled) and at 26 weeks (total enrolled) comparing those in the observational cohort and those in the intervention cohort.
- 2) Biomarkers associated with depression including IL-6 measured from plasma as well as morning cortisol levels at screening and 26 weeks.

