- 5) *Baseline Cytokine Analysis:* As a secondary outcome, subjects will be categorized into baseline groups of mild depression versus moderate or above depression. We will compare baseline plasma biomarker levels by group via linear regression of \log_2 transformed data. Any demographic covariates associated with depression will be included in the regression model. We will also compare by 9 am cortisol levels. We will assess whether age or sex are associated with biomarker responses.
- 6) *Virologic Outcomes:* As a secondary outcome, proportions of those with 26-week virologic suppression will be correlated by those with persisting depression vs. resolved using Fisher's Exact test.
- 7) *Depression Scale Comparison:* We will compare prevalence of depression using the PHQ-9 and the HDRS. We will compare the proportions of those depressed at baseline and 26 weeks using McNemar's test.
- 8) *Social Factors and Stress Assessment:* We will analyze social factors and the STRAIN stress and adversity tool scores by baseline depression groups as well as those with persistent depression at 26 weeks using linear regression.

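### Objective 3 asks whether group psychotherapy improves 26-week viral suppression, but the only planned virologic analysis compares persisting with resolved depression

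*Combined protocol and SAP*

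**What the plan says.** Section 2.1 lists three objectives. The third is: "Evaluate if viral suppression levels at 26 weeks are improved by group psychotherapy". Under section 4.1 the comparison that would answer it is between two groups of depressed participants enrolled one after the other. "The first half of the depressed participants (100 subjects) will be in the observational cohort"; the next 100 receive group psychotherapy.

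Section 8.2, item 6, is the only analysis there with suppression as its outcome: "proportions of those with 26-week virologic suppression will be correlated by those with persisting depression vs. resolved", by Fisher's exact test. The synopsis (Statistical Analysis, item 5) gives the same contrast: "proportions of those with 26-week virologic suppression will be compared by those with persisting depression vs. resolved".

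The item in both lists that is named for the psychotherapy effect (item 1) covers the proportion depressed and the change in PHQ-9, not viral load. Neither of the two endpoints under section 2.1 includes viral suppression. Elsewhere in the analysis items, viral load is named only as a possible adjustment variable.

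**The concern.** Depression status at week 26 is observed after treatment and may itself be changed by psychotherapy. Comparing suppression between persisting and resolved depression describes an association within the pooled depressed participants. It does not estimate what psychotherapy does to suppression.

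The plan's own background makes a false reading plausible. Section 1.2 states: "There is also evidence that depression is associated with poorer levels of viral suppression and even mortality". A clear gap between persisting and resolved participants is therefore to be expected even if psychotherapy has no effect on viral load, and it could be taken as support for Objective 3. The opposite error is also possible: a real cohort difference could pass almost unseen.

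The split also requires a week-26 PHQ-9. Section 8.1 allows up to 5% loss to follow-up, about 10 of 200 participants. Those people cannot be classified, and the documents do not say whether they would still have a viral load on the chart.

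**Working it through.** **1. What the stated sample size covers.** Section 8.1 gives 168, with delta 0.5 (read as 0.5 SD), two-sided alpha 0.05, 80% power and 25% persistent depression. With a 1:3 split of persistent to resolved:

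- smaller group = (1 + 1/3) × (1.960 + 0.842)² / 0.5² = 41.9, rounded up to 42
- total = 42 × 4 = 168

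The figure reproduces, and it belongs to the IL-6 contrast. The documents give no figure for viral suppression, so all suppression rates below are assumptions.

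**2. Inputs on persistence.** For the psychotherapy cohort, section 8.1 says: "Assuming that 25% of the psychotherapy group will have persistent depression at week 26". For the observational cohort I use three values:

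- 38%, from section 1.2: "in this cohort 38% (28/73) had persistent depression at 2 years with HIV therapy alone". This is a two-year CES-D figure, not PHQ-9 at 26 weeks with SSRI referral.
- 50%, an assumption.
- Equal persistence in both cohorts.

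Cohorts are taken as equal in size.

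**3. Scenario A: psychotherapy adds 10 points of suppression in everyone, whatever their depression status.** The planned test sees 10 × (observational share of the persistent − observational share of the resolved).

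- 38% vs 25%: 0.38/0.63 = 0.603; 0.62/1.37 = 0.453; difference 0.151, so **1.5 points**
- 50% vs 25%: 0.50/0.75 = 0.667; 0.50/1.25 = 0.400; difference 0.267, so **2.7 points**
- equal persistence: 0.5 − 0.5 = **0 points**

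The true cohort difference is 10 points in each case.

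**4. Scenario B: 90% suppressed if resolved and 70% if persistent, with no other effect of cohort.** The planned test sees 90 − 70 = **20 points**. The cohort difference is:

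- 38% vs 25%: observational 0.38 × 70 + 0.62 × 90 = 82.4%; intervention 0.25 × 70 + 0.75 × 90 = 85.0%; **2.6 points**
- 50% vs 25%: 80.0% vs 85.0%; **5.0 points**
- equal persistence: **0 points**

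**5. One planned-test table, two answers to Objective 3.** Suppose 35/50 persisting and 130/150 resolved are suppressed (Fisher p = 0.010). With 25 persisting and 75 resolved in each cohort, that table fits both of these:

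| Observational | Intervention | Difference | Fisher p |
|---|---|---|---|
| 82/100 | 83/100 | 1 point | 1.0 |
| 72/100 (12/25 + 60/75) | 93/100 (23/25 + 70/75) | 21 points | 0.0001 |

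The planned result therefore does not determine the psychotherapy contrast.

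**6. What the missing contrast could deliver.** Take 95 per cohort (100 less 5%). The 95% half-width is 1.96 × √(2p(1 − p)/95):

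- p = 0.7: 13.0 points
- p = 0.8: 11.4 points
- p = 0.9: 8.5 points

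For 80% vs 90%, exact power is 49% with the pooled z test and 42% with Fisher's test. From 80%, a difference of about 14 points is needed for 80% power by the normal approximation (82.4% at 14 points). Fisher's exact power at 80% vs 94% is 78.6%, just short.

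**The case against.** Several fair points can be made for the plan.

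- **Text may be missing.** Section 8.2 jumps from item 3 to item 5, and section 8.1 refers to a statistics plan that is not visible. A cohort analysis might have stood in either place. This is unlikely. The synopsis list runs 1 to 7 without a gap, its seven items match the seven in section 8.2, and none compares suppression by cohort. The statistics plan is described as a range of sample sizes.
- **The objective is minor.** Suppression is in neither listed endpoint nor in the hypothesis, both analysis lists call it secondary, and the study is sized for IL-6. This stands, and it limits the severity. It does not remove the contradiction with section 2.1.
- **Item 6 is a legitimate association.** It is, and nothing in the plan says it will be cited for Objective 3. The misreading is a risk, not a stated intention.
- **The magnitudes are illustrative.** True: the 90% and 70% are not from the documents. The conclusion rests on the text; the numbers show only how far apart the two contrasts can lie. The 95 per cohort is also a stand-in, because the relevant loss is missing viral loads, for which there is no figure.
- **The data may be incomplete.** Viral load comes from chart review of routine care, and the week-26 form as reproduced shows no field for it. It is planned in Table 1, but completeness is not assured.

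**Conclusion.** The concern holds. Objective 3 has no planned estimate, and both analysis lists put a different contrast in its place. Under the assumed rates, the planned test would show 0 to 2.7 points when psychotherapy truly adds 10. It would show 20 points when the cohort difference is 0 to 5. The mismatch itself depends on no assumption; only these sizes do.

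This should be fixed before analysis, but it is not fatal. The outcome is secondary, the cohorts are not randomised, and the added contrast would be imprecise. That imprecision is a reason to report an interval, not to answer another question.

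**What to change.** Add an Objective 3 analysis to section 8.2 and the synopsis:

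- **Estimate.** The intervention-minus-observational difference in week-26 suppression among the depressed participants, as a risk difference with 95% confidence interval, adjusted for baseline covariates already recorded (for example CD4, age, sex, clinic).
- **Population.** Everyone in the two depressed cohorts with a chart viral load, with or without a week-26 PHQ-9.
- **Definitions.** State the suppression cut-off, the chart window that counts as week 26, and the handling of missing viral loads. The documents give none of these.
- **Interpretation.** State that enrolment is sequential and not randomised, so calendar time may confound the estimate, and state the expected precision.

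Keep persisting versus resolved as a separate exploratory association, reported by cohort, and do not cite it for Objective 3. If the sponsor does not want a cohort contrast, rewording Objective 3 to match item 6 would also remove the contradiction, at the price of dropping the psychotherapy question for viral load.

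The cost is SAP text, one model and the written definitions. No new measurements are needed, since chart review of viral load is already scheduled. A data field for the value and its date should be confirmed.
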